#### **6.8.10.3. Children's Depression Inventory-2**

The CDI-2 has both a self-report and a parent version. The CDI-2: Self-Report Short version is an efficient screening measure that contains 12 items. The self-report short version will be administered to patients 7 to  $< 12$  years of age according to the SoAs (Table 1, CCI ).

Items on the CDI-2 Parent form correspond to items on the self-report version and are suitably rephrased. Item selection for the parent forms was guided to maximize validity, and thus focused on observable manifestations of depression. The CDI-2 parent form consists of 17 items and the 4 choices provided for each item correspond to 4 levels of symptomatology: 0 (not at all), 1 (some of the time), 2 (often), or 3 (most of the time). The CDI-2 parent version will be administered to caregivers of patients 7 to  $< 12$  years of age according to the SoAs (Table 1, CCI ).

An AE will be recorded for any patient with a CDI-2 T-score  $\geq 65$  and the patient will be referred to an MHP.

The CDI-2 questionnaire should be completed before dosing either in clinic or in the presence of trained nursing or site staff during telehealth visits, as applicable.

### **6.9. Data Safety Monitoring**

The Investigators will be responsible to review and evaluate safety data from their patients in a continuous manner. Cumulative safety data from the trial will be reviewed by the Sponsor on an ongoing basis for any safety signals or tolerability concerns. Additionally, this trial will be monitored by an independent Data Safety Monitoring Board (DSMB). The DSMB will operate under a separate charter and will meet periodically (ie, every 3 months) to review the cumulative safety data from the trial and will make a recommendation to continue or modify the trial, if needed. Details of the DSMB's composition and operations will be in the DSMB charter.

## 6.10. Adverse Events

The definitions of an AE or SAE can be found in [Appendix 5](#). AEs will be recorded from the time a patient provides informed consent/assent. AEs reported after dosing on Day 1 will be considered treatment-emergent AEs (TEAEs).

AE will be reported by the patient (or, when appropriate, by a caregiver, surrogate, or the patient's legally authorized representative).

The Investigator and any designees are responsible for detecting, documenting, and recording events that meet the definition of an AE or SAE and remain responsible for following up AEs that are serious, considered related to the trial treatment or trial procedures, or that caused the patient to discontinue trial treatment (see [Section 4.3](#)).

### 6.10.1. Time Period and Frequency for Collecting AE and SAE Information

All AEs, including SAEs, will be collected from the provision of informed consent/assent until the SFV at the time points designated in the SoAs ([Table 1](#), [CCI](#)). AEs reported after dosing on Day 1 will be considered TEAEs.

Medical occurrences that begin before the start of trial treatment will be recorded on the Medical History/Current Medical Conditions section of the eCRF (not the AE section).

All SAEs will be recorded and reported to the Sponsor or designee within 24 hours, as indicated in [Appendix 5](#). The Investigator will submit any updated SAE data to the Sponsor within 24 hours of it being available.

Investigators are not obligated to actively seek AE or SAE in former trial patients. However, if the Investigator learns of any SAE, including a death, at any time after a patient has been discharged from the trial, and he/she considers the event to be reasonably related to the trial treatment or trial participation, the Investigator must promptly notify the Sponsor.

The method of recording, evaluating, and assessing causality of AE and SAE and the procedures for completing and transmitting SAE reports are provided in [Appendix 5](#).

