**Table 1: Schedule of Assessments**

Trial Period/ Procedure*	Screening	Treatment Period															EOT †† (after 52 weeks on a therapeutic regimen)		ETT	SFV 	Bridging Visits**	
Clinic Visit Number		V1 	Call	V2	V3 †	V4	V5 †	V6 †	V7	V8 †	V9	V10 †	V11	V12 †	V13	V14 †	V15 ††	V16 ††			Every 12 weeks	
Trial Day		-56 to -1	1	8	22	50	78	106	134	162	190	218	246	274	302	330	358	386	414			
Trial Week		-8 to -1	1	2	4	8	12	16	20	24	28	32	36	40	44	48	52	56	60			
Visit Window (days)	-	-	±4	±4	±4	±4	±4	±4	±4	±4	±4	±4	±4	±4	±4	±4	±4	-4 weeks +4 days		±4	±2 weeks	
ADA 		X				X			X								X ††	X	X	X	X	
CCI	X 	CCI																				
Telephone call 			X																		X 	
Dispense/ Return study drug 		X		X	X	X	X	X	X	X	X	X	X	X	X	X	X ††	X	X		X	
Study drug administration 		Daily																		Daily		
Injection site inspection 		X	X	X	X	X	X	X	X	X	X	X	X	X	X	X	X ††	X	X		X	
Drug compliance assessment 		X	X	X	X	X	X	X	X	X	X	X	X	X	X	X	X ††	X	X		X	
Adverse event collection 	Continuous from signing of ICF through completion of trial participation																					

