#### 5.1.3. End of Treatment

The End of Treatment (EOT) visit will occur as an in-person clinic visit after 52 weeks on a therapeutic regimen, which is the final planned week of dosing with trial treatment. At the EOT, patients who complete 52 weeks on a therapeutic regimen and complete assessments through the EOT visit may be eligible to enter an open-label LTE trial or attend Bridging visits with open-label setmelanotide if the LTE is not yet available. Patients must meet the LTE eligibility criteria and should discuss eligibility with the Investigator.

CCI

All patients who discontinue treatment prematurely should attend an ETT Visit as soon as possible after the last dose of trial treatment. Patients who discontinue treatment but remain enrolled in the trial should continue to complete assessments (as Retained Dropouts). These patients will be required to complete the SFV as applicable following the ETT (Section 5.1.4). Patients who discontinue treatment prematurely are not eligible to enroll in the optional LTE trial. Exceptions may be made in consultation with the Sponsor.

Patients who discontinue prematurely and withdraw from the trial will not be required to complete the SFV following the ETT.

If the ETT Visit occurs 4 weeks or later following the last dose of trial treatment, then the ETT Visit will replace the SFV if no AEs are being monitored.

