#### 5.1.4. Safety Follow-up Visit

An SFV will occur as an in-person visit 14 days ( $\pm 4$  days) after the last dose of trial treatment. The SFV is not required for patients who complete the treatment period and either:

- enroll in the LTE (or bridging visits if the LTE is not yet available) or transition to another qualified Rhythm study (e.g., managed access)
- transition to a commercially available Rhythm MC4R agonist regimen

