#### 5.1.6. Completion of Trial Participation

Completion of trial participation for an individual patient is defined as 1 of the following:

- For patients who completed 52 weeks on a therapeutic regimen at the EOT and enroll in the LTE (or Bridging visits) or transition to either commercial drug or a post-trial access program: the EOT Visit

- For patients in bridging visits or who have transitioned from bridging visits to commercial drug or a post-trial access program: the last bridging visit.
- For patients who complete 52 weeks on a therapeutic regimen through the EOT Visit and do not enroll in the LTE, bridging visits, or transition to either commercial drug or a post-trial access program: the SFV
- For patients who prematurely discontinue trial treatment and complete some trial assessments but do not withdraw consent (and assent, as applicable): the latest of the EOT Visit, ETT Visit, or SFV (if required)
- For patients who withdraw consent or assent: date of withdrawal of consent or assent (ETT Visit)

CCI

The end of the trial overall is defined in Section 5.3.

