#### 4.3.1. Primary Estimand

The population of the primary estimand is among participants (aged 4 years or older) with documented evidence of acquired HO and weight gain according to the inclusion/exclusion criteria. Participants will receive either active setmelanotide or placebo, where dose-escalation will occur based upon an **CCI** [REDACTED]. The primary analysis will be executed using the mITT analysis set, including all randomized patients receiving at least one dose of study drug, grouped as randomized.

The variable is mean percent change from baseline in BMI after 52 weeks of treatment with either setmelanotide or placebo.

Intercurrent events: Patients who discontinue treatment prior to study discontinuation will be handled via the treatment policy strategy, in which all collected measurements will be included in the statistical analyses. Other potential intercurrent events such as receiving the wrong treatment, treatment interruption, and non-adherence to study drug will also be handled via the treatment policy strategy whereby all collected measurements will be included in the statistical analyses.

Any on-study death will be handled via the composite strategy, in which death is considered a sufficiently unfavorable outcome and the patient will have their corresponding change and percent change from baseline artificially set to 0.

The population level summary is the difference between treatment groups (setmelanotide and placebo) in mean percent change from baseline in BMI at Week 52, obtained from an analysis of covariance (ANCOVA) model, with unequal variance to account for possible unequal residual variances, based on the outcomes of 100 imputed datasets combined using Rubin's Rule (Little and Rubin 2002). Multiple imputation assuming missing not at random (MNAR) will be used as the primary approach for missing data and will model the missing measurements based on known measurements from retrieved dropouts in the same treatment group. If insufficient retrieved dropouts exist to provide a reliable multiple imputation model, wash-out imputation will be used where missing values for subjects on active drug will be imputed with observed baseline and data from the placebo group. No intermediate values from the active treatment group would be used in this approach. Further technical details are found in [Section 3.10.2](#).

The robustness of the primary estimand will be assessed through sensitivity analysis using two-dimensional tipping point.

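### Adverse-event collection ends at the Safety Follow-up Visit in Protocol Section 6.10.1 but at completion of trial participation in the Schedule of Assessments, and the two dates differ for retained dropouts

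*Protocol*

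**What the plan says.** Two current rules set the end of AE collection.

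- Protocol Section 6.10.1: AEs and SAEs "will be collected from the provision of informed consent/assent until the SFV", with a pointer to the schedule for the time points.
- Protocol Table 1, AE collection row, repeated in SAP Table 1-1: "Continuous from signing of ICF through completion of trial participation".

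Three further provisions fix the dates.

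- Protocol Section 5.1.4: "An SFV will occur as an in-person visit 14 days" (±4) after the last dose. Footnote 2 of Table 1 applies this timing to patients who discontinue early, so their SFV is not deferred to EOT.
- Protocol Sections 4.3 and 5.1.3: patients who stop treatment but stay enrolled go on attending the scheduled visits.
- Protocol Section 5.1.6: for these patients participation is complete at "the latest of the EOT Visit, ETT Visit, or SFV (if required").

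Section 5.1.4 waives the SFV for patients who complete treatment and enter the LTE or Bridging.

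On the analysis side, SAP Section 4.5.2 defines treatment-emergent AEs (TEAEs) up to 14 days after the last dose, and labels that date the end of the study. Events that worsened or were judged drug-related are treated separately. SAP Section 4.3.1 adds: "Any on-study death will be handled via the composite strategy".

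**The concern.** A retained dropout has an SFV about two weeks after stopping drug and may then attend visits for months. Read as written, Section 6.10.1 ends collection of new events at that SFV, while the schedule keeps it open. One site may follow the section text and another the schedule, so the same event in the same kind of patient could be recorded at one site and not at the other.

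The trial keeps following these patients for efficacy. Their weights feed the treatment-policy analysis and the retrieved-dropout imputation in SAP Section 3.10.2, and the estimand's death rule requires deaths to be known up to the primary timepoint. It is odd to follow a patient for efficacy under a rule that may have closed safety collection. The periodic safety review by the data safety monitoring board (Protocol Section 6.9) would also rest on whichever reading each site adopted.

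For patients who go into the LTE or Bridging, a rule that ends at the SFV has no date attached to it at all.

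**Working it through.** The plan states no figure for the length of the discrepancy, so there is none to reproduce. The check is date arithmetic.

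**Inputs.** The SFV falls at the last-dose day + 14, window ±4 (Section 5.1.4). The EOT is at Visit 15, Day 386, window ±4, or Visit 16, Day 414, window −4 weeks to +4 days (Table 1). I assume that a retained dropout attends to one of these nominal EOT days.

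**Formula.** Gap = EOT day − (last-dose day + 14), floored at zero. This is time inside the schedule's collection window but outside that of Section 6.10.1.

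| Last dose (day) | SFV (day) | Gap to Day 386 | Gap to Day 414 |
|---|---|---|---|
| 1 | 15 | 371 days (53 weeks) | 399 days (57 weeks) |
| 22 | 36 | 350 days (50 weeks) | 378 days (54 weeks) |
| 78 | 92 | 294 days (42 weeks) | 322 days (46 weeks) |
| 162 | 176 | 210 days (30 weeks) | 238 days (34 weeks) |
| 274 | 288 | 98 days (14 weeks) | 126 days (18 weeks) |
| 371 | 385 | 1 day | 29 days (about 4 weeks) |

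The gap closes when the last dose is 14 days before EOT: 386 − (372 + 14) = 0, and 414 − (400 + 14) = 0.

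**Visit windows.** For a last dose on Day 1, the earliest Visit 15 with the latest SFV gives 382 − (1 + 18) = 363 days. The latest Visit 16 with the earliest SFV gives 418 − (1 + 10) = 407 days. The windows do not change the picture.

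**Late ETT.** Section 5.1.3 lets an ETT visit held 4 weeks or more after the last dose stand in for the SFV when no AEs are being monitored. If collection is then read as ending at that ETT, the largest gap is 386 − (1 + 28) = 357 days (51 weeks) or 414 − (1 + 28) = 385 days (55 weeks).

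**Where the rules agree or are silent.** For a patient who completes treatment and takes none of the onward routes, Section 5.1.6 ends participation at the SFV, so both rules give the same date. For LTE and Bridging patients there is no SFV, so Section 6.10.1 gives no date, while the schedule and Section 5.1.6 together do.

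**The case against.** The strongest reply is that Section 6.10.1 itself refers sites to the time points in the schedule, and Section 6 makes adherence to the schedule mandatory. A careful site would therefore reach the longer window. This softens the problem, but the sentence still names an explicit earlier stop, and a pointer to time points does not cancel it. The same reply is made for LTE and Bridging patients, and it works only for a site that goes by the schedule.

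A reader might infer that deaths and SAEs after the SFV would simply be lost. The documents do not support that. The 24-hour SAE reporting sentence in Section 6.10.1 has no end date. Its relief from actively seeking events covers former patients only, and retained dropouts are still enrolled. Appendix 5 asks for post-mortem findings when a patient dies during participation. Section 4.4 requires documented contact attempts after a missed visit. These safeguards do much for deaths and something for SAEs, but nothing for new non-serious AEs.

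A reader might also infer serious damage to the primary estimand. The death rule needs only knowledge of the death, which the safeguards above largely supply. As an illustration, suppose one of 80 setmelanotide patients is scored 0 where −10 would otherwise have been used. The arm mean moves by 10/80 = 0.125 points, against a planned difference of 10.

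Finally, a reader might take the 20% dropout assumption as the share of patients affected. It is a sample-size input. The stated power of about 99.5% reproduces with 64 and 32 evaluable patients: the noncentrality is 10/(10 × √(1/32 + 1/64)) = 4.62, and power is 99.55% by the noncentral t. In that calculation the dropouts contribute no endpoint data, so it gives no count of patients retained to EOT.

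It is also fair to say that SAP Section 4.5.2 leaves most late events out of the TEAE tables under either collection rule, and that the documents give no mechanism by which blinded sites would differ by arm. Both points limit the harm to the planned comparison. The first is a further reason to reconcile the SAP.

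**Conclusion.** The contradiction stands in current text and is more than missing detail: a site following Section 6.10.1 literally would stop collecting new events in patients who still attend visits. Per retained dropout the discrepancy runs from zero to about 53–57 weeks at nominal visit days, shortening as the stop comes later. The total cannot be sized, because the expected number of retained dropouts is not given.

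The consequence is uneven ascertainment of AEs and SAEs between sites after early discontinuation. The conclusion assumes that at least some patients stop treatment early and stay to EOT, as the plan encourages, and that some sites take the section text at face value. It is worth correcting, but it does not threaten the primary result.

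**What to change.** In Protocol Section 6.10.1, replace the stop at the SFV with a stop at completion of participation as defined in Section 5.1.6, and state that this includes retained dropouts after their SFV. That matches Table 1 and gives LTE and Bridging patients an end point. Section 5.1.6 mentions Bridging under both the EOT visit and the last Bridging visit, so the revised sentence should say which date applies to them.

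In SAP Section 4.5.2, stop equating 14 days after the last dose with the end of the study. Protocol Section 6.10.1 counts AEs after Day 1 dosing as treatment-emergent with no closing date, so the two definitions need reconciling. Then summarise by randomised arm the SAEs and deaths with onset after the 14-day window and up to EOT, separately from TEAEs.

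The cost is a short protocol clarification, slightly more AE data entry and one extra table. Retained dropouts already attend the visits, so no new procedures are needed.

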### 6.10.2. Method of Detecting AEs and SAEs

Care will be taken not to introduce bias when detecting AEs and/or SAEs. Open-ended and non-leading verbal questioning of the patient or caregiver is the preferred method to inquire about AE occurrences.

### 6.10.3. Follow-up of AEs and SAEs

After the initial AE/SAE report, the Investigator is required to proactively follow each patient at subsequent visits/contacts. All SAEs will be followed until resolution, stabilization, the event is otherwise explained, or the patient is lost to follow-up. Further information on follow-up procedures is given in [Appendix 5](#).

### 6.10.4. Trial Treatment and Stopping Rules for Safety Considerations

Safety parameters will be monitored during the trial. Trial treatment administration will be interrupted if certain safety parameter criteria are met, and additional assessments may be implemented. The Monitoring Plan provides for detailed instructions.

#### 6.10.4.1. Liver Function Tests

The central laboratory will notify the medical monitor of ALT or AST  $\geq 2$  x upper limit of normal (ULN) or total bilirubin  $> 2$  x ULN.

Patients with treatment-emergent ALT or AST elevations of  $\geq 3$  x ULN, with or without total bilirubin  $\geq 2$  x ULN, should interrupt treatment immediately and be followed closely with confirmatory follow-up testing performed by central laboratory within 48 to 72 hours of the initial finding. If a patient cannot come to the site for confirmatory testing, a local laboratory may be used. Local laboratory results may be reported immediately to the medical monitor as soon as possible. A detailed plan for monitoring transaminases, treatment interruption, discontinuation, and treatment resumptions will be provided in the Medical Monitoring plan.

#### 6.10.5. Overdose

An overdose is a significant variation from the recommended/scheduled dosage for a product. For this study, an overdose of setmelanotide is considered a dose higher than:

- CCI [REDACTED]
- [REDACTED]
- [REDACTED]
- [REDACTED]

In the event of an overdose, the Investigator should contact the Medical Monitor immediately. Appropriate supportive treatment should be initiated according to the patient's clinical signs and symptoms.

The quantity of the excess dose as well as the duration of the overdose are to be documented in the eCRF.

Decisions regarding dose interruptions or modifications will be made by the Investigator in consultation with the Medical Monitor based on the clinical evaluation of the patient.

#### 6.10.6. Regulatory Reporting Requirements for SAEs

- Prompt notification by the Investigator to the Sponsor of a SAE is essential so that regulatory obligations and ethical responsibilities towards the safety of patients and the safety of a trial treatment under clinical investigation are met.
- The Sponsor has a legal responsibility to notify both the local regulatory authority and other regulatory agencies about the safety of a trial treatment under clinical investigation. The Sponsor will comply with country-specific regulatory requirements relating to safety reporting to the regulatory authority, IRBs, IECs, and investigators.
- Investigator safety reports must be prepared for suspected unexpected serious adverse reactions (SUSAR) according to local regulatory requirements and Sponsor policy and forwarded to investigators as necessary.
- An investigator who receives an investigator safety report describing a SAE or other specific safety information (eg, summary or listing of SAEs) from the Sponsor will

review and then file it along with the IB and will notify the IRB/IEC, if appropriate according to local requirements.

## 7. STATISTICAL CONSIDERATIONS

This section describes the plans for analysis. Details of the statistical methodology for summaries and statistical analyses will be provided in a separate statistical analysis plan (SAP), which will be maintained by the Sponsor. The SAP may modify the plans outlined in the protocol; however, any major modifications of the primary endpoint definition and/or its analysis will also be reflected in a protocol amendment. If, after the trial has completed, changes are made to the SAP, then these deviations to the plan will be listed, along with an explanation as to why they occurred, in the clinical study report for the trial, as appropriate.

The primary analysis includes the first 120 patients with acquired HO dosed in any region who have completed the trial and any patients with acquired HO who discontinued after receiving their first dose.

A separate double-blind, multi-center, placebo-controlled, randomized sub-study (RM-493-040-A) will be conducted in the United States and the United Kingdom. The sub-study is designed to evaluate the efficacy and safety of setmelanotide on weight loss and hunger in a population of patients with congenital HO aged 4 years and older.

This sub-study in patients with congenital HO will be analyzed and reported separately. Sub-study analyses will be documented in the SAP and a CSR addendum with data from this sub-study will be submitted separately.

CCI

